7.4 Data Analysis

Data analysis for this study will be descriptive in nature. Demographic and clinical characteristics of the sample, as well as post-surgery complications will be summarized using descriptive statistics and the confidence intervals will also be provided.

[figure not shown]
Patients assigned to the intervention group (3D simulation) will be compared with those who had conventional techniques using χ^2 tests for categorical variables and Student's t-tests for continuous variables. For the t-tests equal variances were not be assumed, unless significant by Levene's test. Mann-Whitney U tests will be utilized for non-normally distributed variables. Two-tailed P values 0.05 will be considered statistically significant.

Multivariate analyses for Breast Q scores, mammometric parameters, and patient satisfaction will be performed using binary logistic regression and linear regression models to examine the relationship between intervention groups and examined outcomes and to identify potential confounders. The results of multivariate analyses will be expressed as odds ratios with corresponding 95% confidence intervals. All analyses will be performed using SPSS 20.0 statistical software (SPSS Inc. Chicago, IL).

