4.2 Randomization

100 patients will be recruited in the randomized cohort. Randomization will be performed by a Research Patient Coordinator and the patient assigned to the control group or the intervention group. Randomization will only occur after the patient has signed the informed consent and will be documented in the case report file as well as communicated to the treating surgeon.

Intervention group

In the intervention group, in addition to standard preoperative evaluation, 3D image simulation will be performed.

Control group

In the conventional group, only the standard preoperative evaluation will be performed.

Non-Randomized cohort

In the non-randomized cohort, the patient can choose to have the standard evaluation with the addition of the 3D image simulation or not based on discussion with their surgeon.

Minimizing measurement bias

Blinding of the patient or surgeon will not be possible due to the need for the 3D imaging simulation to be openly discussed and viewed prior to the operation for patients randomized to 3D intervention and for the nonrandomized cohort.

All subjects will be administered the Breast Q questionnaire prior to surgery regardless of assigned group. The questionnaire will take approximately 5-10 minutes of time to complete.

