7.3 Sample Size

Appropriate sample size is calculated based on assumption of difference of 20 percent in patient satisfaction as compared with the control group. This difference is considered clinically relevant based on previous similar studies. A sample size of 100 patients (50 in each group) is considered sufficient to prove this difference, if present (alpha error set at 0.05, power>99 percent).

Approximately 75 patients per year undergo a breast augmentation procedure at Washington University Medical Center. The estimated time frame to randomize 100 patients is approximately 24 months.

Non-randomized cohort

Up to 50 patients will be included in the non-randomized cohort.

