3D Breast Imaging for Cosmetic and Reconstructive Breast Surgery: Does 3D Improve Patient Reported Outcomes in Primary Breast Augmentation?

NCT01964105

AUGUST 27, 2014

The trend of enrolling to the randomized arm of our study will be modeled using the LOGISTIC procedure with maximum likelihood estimation. Predicted probability will be obtained from this model to facilitate clear interpretation of non-linear relationships with time. For patient- level comparisons, the assumption of normality will be examined with the Shapiro-Wilk test after which a t-test or Wilcoxon test will be used as appropriate. When using the t-test, equality of variances will first be examined with the Folded F statistic. The pooled t-test will be used for two populations with equal variances. Otherwise the Satterthwaite t-test will be used. Breast-level comparisons will be performed using generalized estimating equations (GEE) and empirical standard error estimates to account for correlation of left and right breast measurements within the same patient. The Pearson or Spearman correlation coefficient will be used to quantify the direction and magnitude of association between mammometric, Q-Score, and clinical data. Statistical analyses will be performed in SAS, version 9.4, with descriptive statistics analyzed and graphed in Prism 7 for Mac.

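### The Levene rule in protocol 7.4 is reversed, pooling variances when they appear to differ, and it conflicts with the SAP; the exposure is patient-level comparisons in groups of unequal size

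*Protocol*

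**What the plan says.** Protocol 7.4 plans Student's t-tests for continuous variables, with Mann-Whitney U tests where data are not normal. On variances it says: "For the t-tests equal variances were not be assumed, unless significant by" Levene's test. On the significance level it says: "Two-tailed P values 0.05 will be considered statistically significant".

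The SAP applies a Shapiro-Wilk test first. For the t-test in patient-level comparisons, "equality of variances will first be examined with the Folded F statistic". It continues: "The pooled t-test will be used for two populations with equal variances". For the remaining case: "Otherwise the Satterthwaite t-test will be used". Breast-level data go elsewhere: "Breast-level comparisons will be performed using generalized estimating equations (GEE) and empirical standard error estimates".

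Protocol 7.2 and 7.3 fix 1:1 allocation with 50 patients per group. Up to 50 more may join a non-randomised cohort, whose data serve the secondary objective. Under protocol 4.2 these patients may have "3D image simulation or not based on discussion with their surgeon". Protocol 7.1(b) plans a comparison of mammometric parameters between patients who had the simulation and those who did not.

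**The concern.** The null hypothesis of Levene's test is that the variances are equal, so a significant result argues against pooling. The protocol sentence makes a significant result the condition for assuming equal variances, and otherwise uses the unequal-variance test. That is the reverse of the usual rule.

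The SAP runs in the usual direction with a different pre-test. Whenever the two pre-tests agree, the two documents select opposite t-tests for the same data. The text does not say which takes precedence, so the choice is left to whoever runs the analysis.

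The consequence depends on group sizes. With equal groups, the pooled and Satterthwaite t statistics are identical and only the degrees of freedom differ. With unequal groups and unequal variances, the pooled standard error is biased. The test then rejects too often if the smaller group is the more variable, and too rarely if the larger group is.

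**Working it through.** **Reading the two rules side by side**

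| Pre-test result | Protocol 7.4 (Levene) | SAP (folded F) |
|---|---|---|
| Not significant | Unequal-variance t | Pooled t |
| Significant | Pooled t | Satterthwaite t |

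The two columns are opposite in both rows.

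**Inputs.** From the documents: 50 per randomised arm, up to 50 non-randomised patients who choose their own option, two-sided 0.05. Assumed, because the documents give no figure: pre-tests at 0.05, SD ratios between groups of 1.5 to 2, normal data, no dropout. The documents give no type I error figure for either rule that could be reproduced.

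**Possible splits if the cohort is added to the randomised arms.** A choice of 25:25 gives 75:75. A choice of 35:15 gives (50+35):(50+15) = 85:65. A choice of 40:10 gives 90:60. If all 50 choose alike, the split is 100:50.

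**Bias of the pooled standard error.** The true variance of the mean difference is V = s1²/n1 + s2²/n2. The pooled test uses, on average, P = [((n1−1)s1² + (n2−1)s2²)/(n1+n2−2)] × (1/n1 + 1/n2). The approximate type I error is 2 × [1 − Φ(1.96 × √(P/V))].

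- 50:50, SDs 1 and 2: V = 1/50 + 4/50 = 0.100; P = 2.5 × 0.04 = 0.100. The ratio is 1 and the error is 5%.
- 85:65, SDs 1 and 1.5: V = 1/85 + 2.25/65 = 0.0464; P = (228/148) × 0.02715 = 0.0418. √(P/V) = 0.950, error 6.3%.
- 90:60, SDs 1 and 2: V = 1/90 + 4/60 = 0.0778; P = (325/148) × 0.02778 = 0.0610. √(P/V) = 0.886, error 8.3%.
- 100:50, SDs 1 and 2: V = 1/100 + 4/50 = 0.090; P = (295/148) × 0.03 = 0.0598. √(P/V) = 0.815, error 11.0%.
- 100:50, SDs 2 and 1: V = 4/100 + 1/50 = 0.060; P = (445/148) × 0.03 = 0.0902. √(P/V) = 1.226, error 1.6%.

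At these SD ratios Levene's test is significant in most data sets (about 86% to nearly 100%), so the protocol rule nearly always lands on the pooled test.

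**Simulation of the complete rules** (equal means, normal data, mean-centred Levene, at least 40,000 data sets per row):

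| Split | SD ratio, more variable group | Protocol rule | SAP rule | Satterthwaite always |
|---|---|---|---|---|
| 50:50 and 75:75 | 1 to 2 | 4.8–5.2% | 4.8–5.2% | 4.8–5.2% |
| 85:65 | 1.5, smaller | 6.2–6.4% | 5.0% | about 5% |
| 90:60 | 1.5, smaller | 6.8% | 5.0% | 4.9% |
| 90:60 | 2, smaller | 8.3% | 5.0% | 5.0% |
| 90:60 | 2, larger | 2.7% | 4.9% | 4.9% |
| 100:50 | 1.5, smaller | 8.3% | 5.2% | 5.0% |
| 100:50 | 2, smaller | 11.1% | 5.0% | 5.0% |
| 100:50 | 2, larger | 1.8% | 5.1% | 5.1% |

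The simulated protocol-rule figures agree with the hand calculation. The SAP rule is weakest at SD ratios near 1.2, where the folded F often misses the difference. At 100:50 it then reaches about 5.8% with the smaller group more variable, and 4.4% the other way round.

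**Size of the effect in the randomised comparison.** With 50 per arm, t = 2.0 and an SD ratio of 2, the pooled test has 98 degrees of freedom (p = 0.0483). Satterthwaite has 49 × 25/17 = 72.1 (p = 0.0493).

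**The case against.** The case for leaving this alone is substantial. The protocol sentence is visibly garbled, so a drafting slip is more likely than an intended rule. It follows a sentence about patients assigned to the intervention, most naturally the 1:1 arms, where the choice of t-test hardly matters. The stated secondary objective is an association, which the SAP handles by correlation, and breast-level measurements go to GEE. Unequal groups are possible rather than certain. Shapiro-Wilk and the non-parametric branches were not simulated. All of this stands and limits the consequence. It does not remove the reversal or the conflict, because an analyst following protocol 7.4 literally would still select the wrong test.

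Three stronger readings are tempting and are not supported:

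- A reader might infer that the SAP rule is also in error. Its direction is correct, and it stays between about 4.4% and 5.8% in the pooled splits examined. Preferring no pre-test is good practice, but the SAP rule is not a mistake.
- A reader might apply a t-test within the non-randomised cohort alone, for example at 40:10 with an SD ratio of 2, where the protocol rule gives about 15% and the SAP rule about 7%. Neither document plans such a test.
- A reader might conclude that the secondary comparison will have unequal groups. The split is not fixed, and an even choice gives 75:75 with no distortion.

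**Conclusion.** The point holds as an error of direction in protocol 7.4 and an unresolved conflict with the SAP. Both follow from the text and need no simulation.

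The numerical consequence is limited. The primary randomised comparison is not at risk. In patient-level comparisons under 7.1(b) that include the non-randomised cohort, the protocol rule would run at about 6% to 8% for 85:65 to 90:60 when the smaller group is the more variable, and would be conservative (2.7% at 90:60, SD ratio 2) when the larger group is. At 100:50, which requires all 50 to make the same choice, the range is about 2% to 11%. These figures rest on assumed SD ratios of 1.5 to 2, normal data and pre-tests at 0.05. If the variances are equal, there is no distortion at any split.

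**What to change.** Delete the Levene sentence from protocol 7.4 and the folded-F step from the SAP, and state one rule in both documents, for example: *Patient-level two-group comparisons of means use the Satterthwaite (unequal-variance) t-test without a preliminary test of variances; breast-level comparisons use GEE with empirical standard errors as in the SAP.* The restriction to patient level matters: a sentence covering all two-group comparisons would displace the GEE and ignore the correlation between left and right breasts.

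State also which document governs the analysis where the two differ.

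The cost is an edit to each document and a negligible loss of degrees of freedom when variances are equal. Satterthwaite without a pre-test held 4.8% to 5.2% in every normal-data case examined. At a minimum, correct the direction of the protocol sentence to match the SAP.

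### Protocol 7.4 and the SAP offer different analyses of the randomised Breast Q comparison, and neither says which one decides the primary objective

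*Protocol*

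**What the plan says.** Protocol 7.1 makes the Breast Q Augmentation Module the primary endpoint. Protocol 7.3 sets one error rate for the comparison: 50 patients per group "is considered sufficient to prove this difference, if present (alpha error set at 0.05").

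Protocol 7.4 then describes two layers of analysis.

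- **Two-sample tests.** Chi-square tests are for categorical data and t-tests for continuous data. The paragraph ends: "Mann-Whitney U tests will be utilized for non-normally distributed variables. Two-tailed P values 0.05 will be considered statistically significant".
- **Regression.** For Breast Q scores, mammometric parameters and patient satisfaction, the plan uses "binary logistic regression and linear regression models to examine the relationship between intervention groups and examined outcomes". The sentence adds a second aim, finding possible confounders. Results are to be given as odds ratios with 95% confidence intervals.

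Section 7.4 opens by calling the analysis descriptive. It labels no analysis as primary or supportive, and gives neither a covariate list nor a cut-point for any Breast Q scale.

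The SAP is a single paragraph. For patient-level comparisons it checks normality with the Shapiro-Wilk test, "after which a t-test or Wilcoxon test will be used as appropriate". It uses logistic regression only for the trend in enrolment to the randomised arm. It does not mention the Breast Q regressions in 7.4, and it does not say whether it replaces 7.4.

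**The concern.** A two-sample test and a regression on the same scale can disagree. Suppose the t-test gives P = 0.07 and the adjusted model gives P = 0.03. The documents then do not say whether the primary objective was met, and the choice would be made after the data are seen. Choosing a single primary scale would not cure this, because the ambiguity lies within each scale.

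The odds-ratio sentence adds a second difficulty. A linear model of a continuous score yields a mean difference, so the sentence cannot describe every model that 7.4 lists. Taken literally, it implies that scores would be split into two categories at a point the protocol does not give.

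**Working it through.** **1. The plan's own figure.** Section 7.3 states "alpha error set at 0.05, power>99 percent" for an "assumption of difference of 20 percent in patient satisfaction as compared with the control group". No standard deviation or control rate is given, so this can be neither confirmed nor refuted. With n = 50 per arm and a 20-point mean difference, power is Φ(20 / (SD × √(2/50)) − 1.96):

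- SD 23.3: Φ(20/4.66 − 1.96) = Φ(2.33) = 99.0%
- SD 30: Φ(20/6 − 1.96) = Φ(1.37) = 91.5%

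For a 20-point difference in proportions, two-sided power runs from 51.6% (40% v 60%) to 90.4% (79% v 99%). This step shows only that 7.3 does not reveal which analysis it was built on.

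**2. Inputs for the false-positive rate.** From the documents: 50 per arm, 1:1 allocation, two-sided 0.05, and the list of methods in 7.4. Assumed, because the documents are silent: normal scores; preoperative score as covariate; correlation r between preoperative and 6-month score of 0 to 0.7; a cut at the median or 75th percentile for the adjusted logistic model (40th, 60th or 80th when unadjusted); and a rule that any P < 0.05 counts.

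**3. t-test plus linear model.** With arm alone in the model, linear regression repeats the pooled t-test, so the rate stays at 5.0%. With the preoperative score added, the two test statistics correlate under the null at (1 − r²)/√(1 − r²) = √(1 − r²). The chance that at least one exceeds 1.96 in absolute value follows from the bivariate normal distribution:

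| r | √(1 − r²) | P(either < 0.05) | Simulated, median-split runs |
|---|---|---|---|
| 0.3 | 0.954 | 6.4% | 6.4% |
| 0.5 | 0.866 | 7.3% | 7.3% |
| 0.7 | 0.714 | 8.3% | 8.3% |

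Simulation gave 5.3% at r = 0. A further simulation put this pair at 6.1-8.9%.

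**4. Adding a logistic model on a dichotomised score.** Simulated null trials (10,000 to 20,000 per setting), any of three P < 0.05:

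| Setting | Rate |
|---|---|
| All three unadjusted | 7.7-7.8% |
| Regressions adjusted for preoperative score, r = 0 | 8.8-9.2% |
| Adjusted, r = 0.3 | 9.0-9.9% |
| Adjusted, r = 0.5 | 9.7-10.1% |
| Adjusted, r = 0.7 | 10.9-11.3% |

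A further simulation of the adjusted case gave 8.9-11.8%. At 10,000 trials the Monte Carlo standard error near 10% is √(0.1 × 0.9/10,000) = 0.3 points. For reference, independent tests would give 1 − 0.95² = 9.75% (two) and 1 − 0.95³ = 14.3% (three). The choice between t-test and rank test, which both documents make from the data, was not simulated.

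**5. What adjustment buys.** For a true effect of 0.5 SD (an illustration, not a figure from the plan), the noncentrality is 0.5 × √(50/2) / √(1 − r²). It is 2.50 for the t-test, and 2.62, 2.89 and 3.50 for the adjusted model at r = 0.3, 0.5 and 0.7. Power is 70% for the t-test against 74%, 82% and 93%. Simulation gave 69-70% against 72-94%.

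**The case against.** A reader might infer that every Breast Q scale is tested three ways and that the plan therefore carries about a 10% false-positive rate. The documents do not support this. Section 7.4 lists two model types for three groups of outcomes and never says that each scale gets both. Its preceding paragraph matches test to variable type, so linear for continuous and logistic for binary outcomes is a natural reading. That leaves two analyses per scale and a rate of about 5-9%. The 10% figure also needs a cut-point, a covariate and an any-P-counts rule, none of which is written down.

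Three more points favour the plan. The 0.05 criterion closes the two-sample paragraph, so extending it to the regressions is an inference. The confounder aim and the word descriptive suggest a secondary role for the models. The SAP has one test per patient-level comparison, so under the SAP alone the multiple-analysis problem within a scale does not arise.

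All of this limits the size; none of it closes the gap. A suggested role is not a stated one, and an analysis called descriptive in 7.4 sits beside an alpha and a power claim in 7.3. The SAP neither names a primary analysis nor says that it supersedes 7.4. The odds-ratio sentence also pulls against the type-matched reading.

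It is fair to say that naming the SAP's two-sample test as deciding would also resolve the ambiguity with less change. The case for the adjusted model is its power, not that the documents require it.

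**Conclusion.** The point holds as a missing decision rule and a mismatch between protocol and SAP. Neither document says which analysis of the randomised Breast Q contrast settles the primary objective. If any P < 0.05 counted, the false-positive rate for one scale would be roughly 5-12%. The low end is a t-test with an unadjusted linear model. The high end is three tests per scale, with both regressions adjusted for a strongly correlated preoperative score. No single figure in that range is a property of the plan, because covariates, cut-point and the allocation of models to scales are unstated. The odds-ratio wording is a separate error in 7.4 that needs no assumption: it does not fit linear regression.

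**What to change.** Put the same statement in Protocol 7.4 and the SAP:

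- The primary objective is decided by one analysis: linear regression of the 6-month score on assigned arm and preoperative score, or on arm alone for a scale with no preoperative score. The test is two-sided at 0.05, and the result is a mean difference with a 95% confidence interval.
- The t-test, the Mann-Whitney or Wilcoxon test and any logistic model are supportive. They cannot establish the primary objective on their own.
- Odds ratios are reported only for logistic models.

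The SAP should also say how it relates to 7.4. The cost is a few sentences and no new data, since Breast Q is already scheduled before surgery and at 6 months (Protocol 4.2, 4.5 and Appendix B). The downside is that a favourable supportive result can no longer be claimed as the primary result.

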Outcomes research in plastic and reconstructive surgery is more likely to focus on patient reported outcomes than survival. While the plastic surgery literature is replete with surveys focused on judging patient satisfaction, they are infrequently validated or comprehensive. The Breast Q has been established as a validated instrument to provide a quantitative measure of the unique features of patient reported outcomes following breast surgery. This instrument represents the most comprehensive and specific quantitative method for patient self-assessment following breast surgery. Recently, McCarthy and colleagues published, for the first time, patient satisfaction in 41 patients who underwent breast augmentation and were evaluated with the Breast Q. This study found statistically significant improvements following breast augmentation in the "satisfaction with breasts" – 14 item scale, "psychological well-being" – 9 item scale, and "sexual well-being" – 5 item scale. This study does not, however, include information on either the benefits of 3D imaging or the mammometric parameters most closely associated with improved satisfaction. Interestingly, the core scale "satisfaction with care" was not evaluated in this study. While this particular core scale may not have been relevant to a study looking at the overall benefits of breast augmentation, we suspect that it may be highly relevant to the aesthetic surgery patient where the consultation experience is more likely to impact overall patient satisfaction.

This study will evaluate the impact of incorporating 3D imaging during preoperative consultation on patient reported outcomes in primary breast augmentation surgery. 3D imaging can be used to facilitate patient education and surgical planning in the context of breast augmentation. The purpose of this study is to utilize the most objective assessment available for assessing patient satisfaction with breast augmentation - the Breast Q - in a prospective randomized trial. We will evaluate whether 3D imaging used in consultation 1) can improve patient reported outcomes, and 2) whether there are measurable mammometric parameters that are associated with improved patient satisfaction and 3) if utilizing 3D imaging in the pre-operative consultation significantly influences final mammometric parameters compared to patients receiving a traditional consultation that does not involve 3D breast surgical simulation.

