7.0 STATISTICAL CONSIDERATIONS

7.1 Study Endpoints

Primary endpoint

BREAST Q Augmentation Module. This includes 6 core items, each with several sub-items. Of the 6 core items, 3 are recently shown to statistically significantly improve in patients undergoing breast augmentation: 1) satisfaction with breasts 2) psychological well-being 3) sexual well being. A fourth, 4) satisfaction with care, however, may be particularly relevant to the discerning aesthetic surgery patient using 3D imaging in consultation. The other core items in this instrument are 5) physical well-being and 6) satisfaction with overall outcome which will also be recorded.

Secondary endpoints

All patients will undergo standard 2D as well as 3D imaging before and after surgery. During consultation, and in the postoperative period, reviewing 3D imaging and morphing software will be unique to the experimental group. 3D imaging from all patients will be used to obtain mammometric data. Pre- , and post- op mammometric data (volumes, vectors, surface distances, anatomic landmarks), as well as the measurable change in these parameters before and after surgery will be correlated with changes in Breast Q patient reported outcomes scores. This will enable us to identify particular mammometric parameters that are a) associated with improved patient reported outcomes and b) determine whether certain mammometric parameters are significantly different in patients who had 3D image simulation as part of their preoperative consultation relative to those that did not.

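### Protocol 7.4 reports every multivariate result as an odds ratio, which does not fit the linear regressions it names, so the scale of the adjusted Breast Q and mammometric results is undefined

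*Protocol*

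**What the plan says.** Protocol Section 7.4 announces "Multivariate analyses for Breast Q scores, mammometric parameters, and patient satisfaction", to be carried out "using binary logistic regression and linear regression models to examine the relationship between intervention groups and examined outcomes". It does not say which outcome goes to which model. The next sentence sets the reporting scale for all of them: "The results of multivariate analyses will be expressed as odds ratios with corresponding 95% confidence intervals".

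The outcomes concerned are mainly quantitative. Section 7.1 gives the primary endpoint as "BREAST Q Augmentation Module. This includes 6 core items, each with several sub-items", with no responder definition or cut-point. Section 1.0 calls the Breast Q a "validated instrument to provide a quantitative measure of the unique features of patient reported outcomes following breast surgery". The mammometric data in Section 7.1 are volumes, vectors, surface distances and landmarks.

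For the unadjusted group comparison, Section 7.4 provides for comparison "using χ^2 tests for categorical variables and Student's t-tests for continuous variables" and adds that "Mann-Whitney U tests will be utilized for non-normally distributed variables". The SAP keeps the same approach at patient level (t-test or Wilcoxon). It adds GEE for breast-level data and correlation coefficients for associations. Its only logistic model concerns how enrolment into the randomised arm changed over time.

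**The concern.** A linear model estimates a difference in means, in the units of the score. An odds ratio is not among its outputs, and exponentiating the coefficient does not make it one. An analyst who follows the reporting sentence therefore has two options for a Breast Q scale: mislabel a linear coefficient, or split the score and use the binary logistic model.

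The second option discards information and leaves the cut to be chosen at analysis. That matters more here because Section 4.2 says neither patient nor surgeon can be blinded. At stake are the interpretability and precision of the adjusted estimate of the 3D simulation effect on the primary endpoint, and of the adjusted mammometric results.

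**Working it through.** **1. The texts side by side (Protocol 7.4 and the SAP).**
- Models named: binary logistic and linear.
- Reporting scale named: odds ratio only, without exception.
- Binary logistic regression gives log-odds coefficients, and exponentiating them gives odds ratios. The rule fits.
- Linear regression, E(Y) = a + b·group + covariates, gives b, an adjusted mean difference. The rule does not fit.
- Cut-point or responder definition: none in either document.
- Multivariable Breast Q model in the SAP: none.

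**2. The plan's only power figure.** Section 7.3 claims power above 99% with 50 per group for a 20 percent difference, alpha 0.05. It gives no SD or control rate and does not say whether the difference is in means or proportions, so the figure can only be bracketed (normal approximation, two-sided).
- Means: the smallest standardised difference with 99% power is (1.960 + 2.326) × √(2/50) = 0.857. If 20 percent means 20 points, the SD may be at most 20/0.857 = 23.3.
- Proportions: an absolute difference of 20 points gives 51.6% to 92.7% power for control rates from 0 to 0.8. A relative difference of 20% gives at most 69.8% for control rates up to 0.8.

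The stated power can be reached on a continuous scale but not on these binary readings. The sample-size section therefore gives no support for a planned dichotomy.

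**3. Cost if a cut were applied.** Assumptions, none from the documents: normal scores, equal SDs, one cut, no covariates. The asymptotic relative efficiency of a cut at quantile q, with c the corresponding normal deviate, is φ(c)² / [q(1 − q)]. At the median this is 0.1592/0.25 = 2/π = 0.637.

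| Split | Efficiency | Loss | Patients needed to match 100 |
|---|---|---|---|
| 50/50 | 0.637 | 36.3% | 158 |
| 40/60 | 0.622 | 37.8% | 161 |
| 30/70 | 0.576 | 42.4% | 174 |
| 20/80 | 0.490 | 51.0% | 205 |
| 10/90 | 0.342 | 65.8% | 293 |

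**4. The same cost as power, 50 per arm.** The t-test uses the noncentral t. The median split uses exact enumeration of the uncorrected chi-square, with success probabilities Φ(d/2) and Φ(−d/2).

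| True effect d (SD units) | Whole score | Median split |
|---|---|---|
| 0.5 | 69.7% | 53.3% |
| 0.6 | 84.4% | 68.4% |
| 0.8 | 97.7% | 89.7% |

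The normal approximation gives 70.5% against 50.6% at d = 0.5. The exact figures are the kinder to splitting, because the uncorrected chi-square has a true size of about 5.7%. At d = 0.857, the effect implied by 99% power, the approximation gives 99.0% against 92.5%.

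**The case against.** The strongest reply is that this is a drafting omission. On that view the writer meant odds ratios for the logistic models and left out the linear coefficients, and naming linear regression at all shows that some outcomes stay continuous. That is the likeliest explanation, and it makes the correction easy. It does not make the sentence usable, since outcomes are not assigned to models and the rule has no exception.

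Two stronger readings are tempting, and the documents do not support them.

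- A reader might infer that the primary endpoint loses about a third of its information. No section dichotomises the Breast Q, and the unadjusted group comparison keeps the whole score in both documents. Neither document calls the regression the primary analysis. The 36% is the best case of a step nobody has planned.
- A reader might infer that an odds ratio is impossible without a cut. A proportional-odds model gives one for an ordered score with no single cut. The protocol does not name that model, so the statement holds only for the two models it does name.

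It is also fair to object that the power comparison is unadjusted while the rule concerns adjusted models, so the figures are indicative only. Finally, if the SAP alone governs, the sentence has little effect. The question then becomes whether the multivariable analysis is done at all, which the two documents leave open.

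**Conclusion.** The point holds for the adjusted analysis. Section 7.4 sets a reporting rule that is wrong for linear regression, one of its two named models, and the SAP has nothing to put in its place. What is certain is the mismatch itself, which needs no assumption. The size is conditional: zero loss if the linear models are reported as mean differences, and about 36% or more if the score is cut, assuming normal scores and a single cut. Severity is minor to moderate: the unadjusted comparison is untouched, but the rule governs the only adjusted estimate of the primary endpoint that either document plans.

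**What to change.** Replace the reporting sentence in Section 7.4 with text such as:

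> Breast Q scale scores and mammometric parameters are analysed as continuous outcomes by linear regression of the 6-month value on randomised group, with the preoperative value of the same measure as covariate where it exists, and reported as adjusted mean differences with 95% CIs. Odds ratios with 95% CIs are reported only for binary outcomes such as complications.

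Add the same model to the SAP. For measurements taken on each breast, the SAP's GEE approach with an identity link gives the same kind of estimate. If the team does want a binary Breast Q outcome, its cut should be fixed and justified in advance as a supplementary analysis.

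The preoperative covariate goes beyond what is needed to cure the mismatch. It is worth including because it usually improves precision, and the Appendix B schedule already collects the questionnaire and the 3D images at screening and at 6 months. The cost is a short wording change in the protocol and a short addition to the SAP, with no new data or visits.
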